8.6.3 Change from Baseline in Plasma Levels of 5-HIAA at Each Study Visit

Fasting (of at least 6 hours) blood samples, for measurement of 5-HIAA in plasma, will be collected and analyzed by a specialty laboratory based on the scheduled of visits in [Table 1](#).

The change from Baseline in plasma 5-HIAA levels will be analyzed using a MMRM. The model will use the change from Baseline in plasma 5-HIAA levels as the dependent variable, and will include patient as a random effect, Baseline plasma 5-HIAA levels as a covariate, time as fixed effect. The Kenward-Roger approximation will be used to adjust the denominator degrees of freedom. A first-order heterogeneous autoregressive covariance structure will be assumed initially to model the within-patient errors; however, other covariance structures will be tested and may be used in the final model if a better fit is evident. The LS means, a 95% 2-sided CLs and the p-values of LS means at each visit will be reported for each study visit to evaluate the treatment effect. A sample SAS code for the model is shown below.

*USUBJID: unique patient ID
AVISITN: analysis visit (eg, week 12, 24, 36, 48, 60, 72, 84 and follow-up visit)
PLA5HIAA: Baseline plasma 5-HIAA levels
RESP: non-count data (eg, change from Baseline in plasma 5-HIAA level)

```
ods output lsmeans=estimates;  
proc mixed data=adev method=reml;  
  class USUBJID AVISITN;  
  model RESP = PLA5HIAA AVISITN / ddfm=kr;  
  repeated AVISITN / subject=USUBJID type=ARH(1);  
  random intercept / subject=USUBJID;  
  lsmeans TRT01PN*AVISITN / cl;  
run;  
ods output close;
```

Lexicon Pharmaceuticals, Inc.
[name]
[name]

1003157

Lexicon Pharmaceuticals, Inc.

LX1606.302

Final V1.0

Statistical Analysis Plan

Descriptive summary statistics will be provided for the observed value and change from Baseline value of the plasma 5-HIAA levels. A graphic display of the parameter estimates and the 95% CLs for the plasma 5-HIAA levels over time will be provided.

Friedman's test for repeated measures will be used to supplement the MMRM, which is similar to that applied in Section **Error! Reference source not found.****Error! Reference source not found.**

9 SAFETY

Statistical analysis of the safety data will involve examination of the descriptive statistics and individual patient listings for any effects of study treatment on clinical tolerability and safety. Safety will be evaluated from concomitant medications, study drug exposure, TEAEs, SAEs, deaths, physical examinations, ECG, clinically laboratory test results, and vital signs. Reporting of these data will be based on the SAF population. Summaries will be prepared by treatment group (corresponding to the LX1606 dose given on Day 1), pooled across all patients, and as needed, by study visit. All safety data will be listed.

9.1 STUDY DRUG EXPOSURE

Duration of exposure in weeks will be summarized using descriptive statistics by treatment group for the SAF. A listing including study drug administration information from the eCRF will be presented.

The numbers of actual dose taken in tablets, expected dose in tablets, and compliance during the study are recorded on eCRF, and will be summarized using descriptive statistics by treatment group for the SAF.

Statistical Analysis Plan

9.2 ADVERSE EVENTS

Adverse event is defined as any untoward medical occurrence associated with the use of a drug in humans, whether or not considered drug related. Treatment-emergent AEs are defined as any AEs not present at before first administration of study drug, but occurring after the start of study drug, or if existing before first administration of study drug, increasing in intensity after initiation of study drug. Since this study provides continued access to telotristat etiprate after patients have completed the required study visits in Phase 2 and Phase 3 studies, all AEs reported in this study will be considered TEAEs. Treatment-emergent AEs will be coded by SOC and PT using the MedDRA, version 15.1. All reported TEAEs will be listed, and the verbatim term will be included in the AE listings.

An overall summary of TEAEs will provide, by treatment group and overall, the number and percentage of patients who reported:

- Any TEAE
- Any treatment-related TEAE (definitely related, possibly related, or probably related)
- Any serious TEAE (SAE)
- Any treatment-related SAE
- Any TEAE leading to study drug discontinuation
- Any TEAE leading to study discontinuation
- Any TEAE leading to death

A set of summary tables of TEAEs by SOC and PT will also be presented for the following categories.

- TEAEs
- TEAEs experienced by $\geq 5\%$ of patients in any treatment group
- Severe TEAEs
- Treatment-related and severe TEAEs
- TEAEs leading to study drug discontinuation
- TEAEs leading to study discontinuation
- SAEs
- TEAE of special interests

1003157

Lexicon Pharmaceuticals, Inc.

LX1606.302

Final V1.0

Statistical Analysis Plan

- Treatment-related SAEs
- TEAEs resulting in death

In addition, TEAEs will be summarized separately by the intensity and relationship to study drug. An additional summary of TEAEs will be presented by PT, but not by SOC. This table will be sorted in descending order of overall number of patients reporting PT.

In the summary tables patients may be counted under multiple SOCs and PTs, but for each SOC and PT, patients are only counted once. If a patient has the same AE on multiple occasions, the highest severity (severe > moderate > mild) or drug relationship (definitely related > probably related > possibly related > not-related) recorded for the event will be presented. If severity of AE is missing in the database, it will be programmed to be 'severe' for the counts in the summary table. If drug relationship is missing then the AE will be considered as 'related' for the summary table.

Central nervous system events of special interest may include any clinically significant changes in mood, physical affect, or exacerbation of preexisting central nervous system conditions, for example, depression and migraine headaches. Patients will be evaluated beginning at Baseline Day 1 and at each subsequent visit for indications of depression. During each visit the patient will first be asked to respond to the question "During the past month, have you often been bothered by feeling down, depressed, or hopeless?" Followed by "During the past month, have you often been bothered by little interest or pleasure in doing things?" A positive response prior to Baseline Day 1 dosing will be captured on the medical history eCRF page. Positive responses following the first dose will be captured as a TEAE and will be followed as a TEAE of special interest.

Listings will be provided for all TEAEs, SAEs, TEAEs leading to study drug discontinuation, TEAEs leading to study discontinuation, deaths, and TEAEs of special interest.

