2.2 TIMINGS OF ANALYSES

The study will be analyzed and reported in 2 phases. The first report will summarize data obtained from all patients providing information up to a specified data cut-off point. The second report will update the initial report by including data from the remaining portion of the study. The first reporting of the data may be taken as an interim analysis in terms of the procedural efforts needed to summarize these data, but it will not serve as a means to modify the analysis/study conduct.

An independent Data Safety Monitoring Board (DSMB) will be charged with reviewing interim safety data on a quarterly basis and reporting its recommendations to Sponsor. Appropriate procedures will be detailed in a DSMB charter that defines accessibility and disclosure of the interim safety results.

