3 STUDY OBJECTIVES

3.1 PRIMARY OBJECTIVE

The primary objective of the study is to evaluate the long-term safety and tolerability of orally administered telotristat etiprate.

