6.3 SAFETY POPULATION

The SAF consists of all patients receiving any fraction of a dose of telotristat etiprate during the study.

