7 GENERAL ASPECTS FOR STATISTICAL ANALYSIS

7.1 GENERAL METHODS

Statistical methodology and analyses are in accordance with the principles outlined by the International Conference on Harmonisation (ICH) E9 guidelines^[1].

Patient listings of all data represented in the electronic case report form (eCRF) will be provided. Measurements from patients excluded from the predefined analysis populations or extra measurements (such as unscheduled or repeat assessments) will not be included in summary tables unless specified otherwise, but will be included in the patient listings. In general, the patient listings will be sorted by treatment group,

1003157

Lexicon Pharmaceuticals, Inc.

LX1606.302

Final V1.0

Statistical Analysis Plan

patient number, and assessment date (and time), if applicable. For most summary statistics, data will be analyzed and displayed by the order of the treatment groups and overall, where treatment groups correspond to how patients were dosed on Day 1 of this study.

Unless otherwise specified, continuous/quantitative variables will be summarized using descriptive statistics, which will include the number of patients with data to be summarized (n), mean, standard deviation (SD), median, minimum, and maximum. The same number of decimal places as in the raw data will be presented when reporting the minimum and maximum, 1 more decimal place than in the raw data will be presented when reporting the mean and median, and 2 more decimal places than in the raw data will be presented when reporting the SD.

All categorical/qualitative data will be presented using frequency counts and percentages. The total number of patients in the treatment group overall (N) will be used as the denominator for percentage calculations, unless stated otherwise in the table shell. All percentages will be presented as 1 decimal point, unless otherwise specified. Percentages equal to 100 will be presented as 100%, and percentages will not be presented for zero frequencies.

All statistical tests will be 2-sided and have an associated α -level = 0.05 unless mentioned otherwise. Confidence limits (CLs) will be 2-sided and calculated with a 95% confidence coefficient.

All statistical analyses will be done using SAS statistical software version 9.3 or higher.

In the case of multiple or repeat assessments at a scheduled visit, the latest value at the visit will be used for summarization and analyses.

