16 APPENDICES

Attachment 1: Table shells

Attachment 2: Listing shells

Attachment 3: Figure shells

Note to File

Subject: Addendum to Statistical Analysis Plan for Studies LX1606.301, 302, 303, and for the LX1606 Integrated Safety Summary (ISS)

RE: Calculation of Extent of Exposure for Open Label Phases of Studies LX1606.301 and LX1606.303, and Study LX1606.302, and in the LX1606 ISS

Date: November 3, 2015

CC: Lexicon- [REDACTED]
[REDACTED] INC- [REDACTED] Ipsen- [REDACTED]
[REDACTED] InStat Services: [REDACTED]

Background:

This note to file is intended to document the methodology to be used in estimating duration of exposure to LX1606 in the above studies and in the ISS for the interim summaries of data which are being provided for inclusion in regulatory submissions.

Study 302 and the Extension Periods of Studies 301 and 303 The referenced studies all provide open label treatment of 500 mg tid for all patients In these studies, the electronic Case Report Form (eCRF) design includes a single page (Study Drug Accountability Extension Period; SDAEP) which records information about study drug administration during the open-label period, including first dose date, last dose date, and compliance calculation. The SDAEP eCRF is intended to be completed when the patient completes or terminates early from the study. Because many of the patients in the open-label studies are currently continuing treatment, and will not have completed SDAEP forms, it is not possible to accurately estimate study drug exposure based on these pages for such patients.

Plan:

The following approach has been agreed:

- Where the SDAEP eCRF includes both the first dose and last dose dates, the patient's duration of open label treatment exposure will be calculated using these dates. If the page also includes study drug compliance information, these patients will also be included in the reporting of study drug compliance.
- Any patient without a last dose date will have their duration of exposure estimated by using the date of the last recorded visit in the eCRF (scheduled or unscheduled), up to and including the week 48 visit (ie, excluding Follow Up visits). The time on study drug will be estimated for these patients, but no estimation will be performed that includes study drug compliance, dose, or amount of drug received during the study.

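### Section 9.2 reports every TEAE category only as a crude percentage of treated patients, so the primary long-term safety objective has no planned measure of event rate or of onset over time

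*SAP*

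**What the plan says.** SAP section 3.1: "The primary objective of the study is to evaluate the long-term safety and tolerability of orally administered telotristat etiprate". No other primary objective is given.

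Section 9.2 opens its tables with: "An overall summary of TEAEs will provide, by treatment group and overall, the number and percentage of patients who reported", followed by seven categories. Ten tables by system organ class and preferred term follow, including one restricted to TEAEs in at least 5% of a treatment group. The counting rule is that "for each SOC and PT, patients are only counted once". Section 7.1 sets the default denominator: "The total number of patients in the treatment group overall (N) will be used as the denominator for percentage calculations". Section 6.3 requires no minimum follow-up: "The SAF consists of all patients receiving any fraction of a dose of telotristat etiprate during the study".

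On follow-up, section 4.1 lets Phase 2 patients enter once the protocol is approved locally and Phase 3 patients enter at their Week 48 visit. Table 1 schedules visits to Week 84. Section 2.2 says of the reporting: "The first report will summarize data obtained from all patients providing information up to a specified data cut-off point"; a second report adds the rest. The note to file of 3 November 2015, appended to the SAP and written for interim summaries intended for regulatory submissions, says that "many of the patients in the open-label studies are currently continuing treatment". The note of 23 November 2015 maps the end-of-study visits of patients who discontinued to analysis visits, with windows starting at Day 42.

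Section 9.1 summarizes duration of exposure by treatment group, separately from the adverse event tables.

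**The concern.** A percentage over all treated patients equals the risk to Week 84 only if everyone is observed to Week 84. Here a patient who entered shortly before the cut-off, or who stopped early, counts in the denominator exactly like one followed for the full period. Nothing in the 9.2 tables uses the onset date, so they cannot show whether new events accumulate, level off or appear late, which is the main question for a long-term extension. A reader of the first report who takes the percentages as cumulative risk to Week 84 would read them too low, most of all for late events. The table of TEAEs in at least 5% of patients could also lose terms whose risk to Week 84 is well above 5%.

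**Working it through.** The SAP gives no event, drop-out or accrual rate, so it has no figure to reproduce. What follows is an illustration. Only the 84 weeks (Table 1) comes from the document; the rest is assumed and shown as a range.

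**Inputs.** R is the true 84-week risk, taken as 10% or 20%, with constant weekly hazard h = -ln(1-R)/84. d is the share discontinued by Week 84, taken as 0 to 60%, with constant rate c = -ln(1-d)/84, independent of the event.

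**Expected crude proportion with potential follow-up t:** p(t) = h/(h+c) × [1 - exp(-(h+c)t)].

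**Final report (t = 84).** Here exp(-84(h+c)) = (1-R)(1-d). For R = 20%, 84h = 0.2231:
- d = 0: 20.0%
- d = 20%: 84c = 0.2231; 0.5 × (1 - 0.8 × 0.8) = 0.180
- d = 40%: 84c = 0.5108; 0.2231/0.7340 × (1 - 0.8 × 0.6) = 0.3040 × 0.52 = 0.158
- d = 60%: 84c = 0.9163; 0.2231/1.1394 × (1 - 0.8 × 0.4) = 0.1958 × 0.68 = 0.133

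**First report, with t spread uniformly over 0-84 weeks.** Averaging p(t) gives h/(h+c) × {1 - [1 - (1-R)(1-d)]/[84(h+c)]}. For R = 20%:
- d = 0: 1 - 0.20/0.2231 = 0.104
- d = 20%: 0.5 × (1 - 0.36/0.4463) = 0.097
- d = 40%: 0.3040 × (1 - 0.52/0.7340) = 0.089

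**Late event.** Set the hazard to zero up to Week 48 and let R = 20% arise between Weeks 48 and 84, so that h' = -ln(0.8)/36. For t > 48, p(t) = exp(-48c) × h'/(h'+c) × [1 - exp(-(h'+c)(t-48))]; otherwise it is 0.

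| True risk to Week 84 | Report | d = 0 | d = 20% | d = 40% | d = 60% |
|---|---|---|---|---|---|
| 20%, constant hazard | final | 20.0% | 18.0% | 15.8% | 13.3% |
| 20%, constant hazard | cut-off | 10.4% | 9.7% | 8.9% | not run |
| 10%, constant hazard | final | 10.0% | 9.0% | 7.9% | 6.6% |
| 10%, constant hazard | cut-off | 5.1% | 4.7% | 4.3% | not run |
| 20%, after Week 48 only | final | 20.0% | 16.8% | 13.5% | not run |
| 20%, after Week 48 only | cut-off | 4.4% | 3.8% | 3.1% | not run |

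So a term with a true 10% risk sits at or just under the 5% threshold at such a cut.

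**Can person-time be formed from the plan as it stands?** Not correctly. For patients without a last dose date, the 3 November 2015 note takes exposure to the last recorded visit but no later than the Week 48 visit. That note covers studies 301, 302 and 303 together, whereas study 302 runs to Week 84. For a patient last seen between Weeks 60 and 84, actual time is 60/48 = 1.25 to 84/48 = 1.75 times the capped time. A rate on the capped basis would be too high, and such patients would be missing from the denominators of intervals after Week 48.

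**Can onset dates be used?** Section 7.4 restricts imputed adverse event dates to deciding treatment emergence, so the plan does not yet allow them to assign an interval.

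**The case against.** The strongest reply is that this is a descriptive, uncontrolled study and the plan is not blind to time. Section 9 allows safety summaries by study visit as needed, section 9.1 summarizes exposure, section 8.1 lists start and stop dates, all TEAEs are listed, and laboratory, vital sign and ECG data are summarized by visit. That is true, but none of it is a planned adverse event rate or onset table: 9.2 lists its tables and none has a time dimension. Section 7.1 lets a table shell set another denominator, and the shells are not available here, but 9.2 announces no such departure.

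Three further replies stand and limit the point.

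- The second report adds the remaining data, so the effect of the cut-off is confined to the first report. What remains comes from early discontinuation, and its meaning depends on the target. If drop-out is independent censoring, 15.8% understates a 20% risk. If discontinuation or death is a competing event, which is plausible since section 8.6 says most patients may have progressive disease, the crude proportion after complete follow-up is the observed on-study cumulative incidence. A reader might infer that the final percentages are biased downward in general; the SAP does not support that.
- A reader might infer that the dose columns are not comparable because follow-up differs between them. Nothing in the SAP says that follow-up differs by dose, and the number of columns is itself unclear. The 3 November 2015 note says all patients receive 500 mg tid, while sections 4.1 and 4.6 and the 23 November 2015 note keep patients on the parent-study dose. Those passages must be reconciled. If there are several columns, comparison is already limited by non-randomized entry and by labelling patients by Day 1 dose.
- The statement that many patients were still on treatment describes the three open-label studies together, with no number for study 302. Follow-up as short as days is only an inference from section 6.3.

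**Conclusion.** The point holds in limited form. The plan gives its sole primary objective, to "evaluate the long-term safety and tolerability of orally administered telotristat etiprate", no measure of adverse event rate or onset over time, although unequal follow-up is built into the design. At the cut-off, the crude percentages understate cumulative risk to Week 84. In the scenarios above with a constant hazard and a 20% risk, they show roughly half of it (8.9% to 10.4%). For an event confined to the period after Week 48 they show about a sixth to a fifth (3.1% to 4.4%). In the final report the shortfall is zero without drop-out. With 20 to 60% drop-out and a 20% risk it is 2.0 to 6.7 percentage points, and only if drop-out counts as independent censoring.

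All these sizes rest on assumed hazards, drop-out and accrual; the SAP supports the direction at the cut-off, not the amount. This is a cheap improvement that should be made. It does not invalidate the crude tables, and it does not extend to comparability between dose columns unless follow-up is shown to differ between them.

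**What to change.** In section 9.2, for overall TEAEs, SAEs, TEAEs leading to discontinuation, deaths, TEAEs of special interest and preferred terms in at least 5% of patients:

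1. Add the number of patients with a first event per 100 patient-years at risk, with 95% CL.
2. Add a table of first-onset TEAEs by interval, for example Weeks 0-24, >24-48, >48-72 and >72-84, with patients still at risk at the start of each interval as denominator. This table is needed as well because a pooled rate is one average and cannot show late risk.
3. Footnote the crude percentages as unadjusted for unequal follow-up.

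Two changes must come first. For study 302, time at risk for patients without a last dose date should run to the last recorded on-treatment visit or to the data cut-off (one of these, fixed in advance) and should not stop at Week 48. Section 7.4 needs a sentence allowing imputed start dates to be used for interval assignment. Separately, the SAP should reconcile its passages on dose, so that it is clear how many treatment columns there are.

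The cost is two extra tables and these two short text changes. The downside is an assumed interval for events with partial onset dates. Section 7.4 sets a missing day to the first of the month and a missing day and month to January 1st (or to the first dose date if later), so such events tend to fall in too early an interval; their number should be footnoted. The note of 5 February 2016 records that interim GI.NET21 outputs for study 302 were finalized on 22 January 2016. If the interim safety tables are also final, the additions would be a supplement to that report and a planned part of the later one.

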9.3 LABORATORY EVALUATIONS

Laboratory results will be reported in standard international system (SI) of units in all TLFs. Clinical laboratory test results (hematology, chemistry, urinalysis, and CgA) and their changes from Baseline value will be summarized by treatment group and analysis visit using descriptive statistics. The laboratory test results (hematology, chemistry, and urinalysis) will be reported as "High", "Low", or "Normal" with respect to relevant reference ranges. A shift table comparing the laboratory test results over the analysis visits to Baseline measure will be presented.

1003157

Lexicon Pharmaceuticals, Inc.

LX1606.302

Final V1.0

Statistical Analysis Plan

All laboratory data will be listed. The laboratory results falling out of the normal range will be marked as “High” or “Low” in the listings. Pregnancy results will be presented in patient listings only.

